This research targets 174 parent/child dyad from the medically underserved Dan River Region. The primary end point is childhood BMI z-scores at 6-months. Families will be identified through medical chart review from the SOVAH Pediatrics (formerly Children's Health Care Center) and PATHS in Danville and Chatham, VA, as well as through responding through local advertisements or flyers. Inclusion criteria include a child between 5-12 years old with a BMI percentile that is 85% or greater for their age

IRB-HSR # 19748: A randomized-controlled trial to compare the reach, effectiveness and maintenance of two family-based childhood obesity treatment programs in a medically underserved region

and gender, live in the Dan River Region, are English speaking, and parents/caregivers ≥ 18 years of age who provide informed consent.

Secondary aims are to determine (1) reach/representativeness, fidelity, and implementation costs, (2) community capacity for implementation and sustainability, (3) relative impact on family eating/physical activity and parental weight, and (4) relative adherence and potential dose response relationships.

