The Challenge of Adherence and Maintenance (RQ1). When examining FBCO interventions, those that include 26-75 contact hours or more are typically the most successful in reducing weight status.³⁴ However, programs that include a high number of contact hours over 6 months are associated with low adherence.³⁵ In healthcare-based pediatric weight management programs, it is typical to see 60 to 70% attrition over the course of a 6-month (or shorter) program.³⁵⁻³⁹ Barlow and Ohlemeyer studied a clinically available weight management program and documented 60% attrition over the course of the program.⁴⁰ Through follow-up with families that had discontinued the program they found that nearly half indicated that it was too difficult to schedule or that the program was too far from home. These findings align with a review of childhood obesity treatment programs that found family difficulty in attending sessions due to competing time demands as the most prevalent reason for low adherence.⁴¹ This lack of adherence is problematic given the consistent finding that higher adherence to treatment protocol is associated with higher likelihood of success.^{42,43}

Compounding adherence issues is a trend for child weight status reductions to move towards baseline values, with a few exceptions,^{21,24} once a FBCO intervention is completed.^{29 44-47} As a result, several research teams have developed and tested FBCO maintenance interventions—with notable results. First, one study demonstrated that a 5 month FBCO intervention followed by 4 months of weekly family sessions using social facilitation practices sustained the initial reduction of ~0.20 in BMI z-score up to 18 months post maintenance intervention.⁴⁸ Another study, that included 15 family group sessions and 10 family counseling sessions over 2 years, found that parent led self-help groups were just as effective at maintaining child BMI z-score reductions at 24 months when compared to a therapist delivered intervention (~0.17 vs 0.18 reduction, respectively)⁴⁹. Finally, when relapse prevention was addressed with only 3 monthly

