iChoose+. *iChoose+* is conceptualized to more accurately reflect the contact frequency and program duration of *Bright Bodies* which included weekly nutrition (parent/child together), behavioral (parent/child independently), and exercise (2/week; child only) session for 24 weeks. For an additional 24 weeks all *Bright Bodies* sessions continued to be delivered, but on a bi-weekly schedule. *iChoose+* will contain the following components: (1) Clear communication *iChoose* workbooks for parents and children that provide the basis for all *iChoose* activities to assist families in changing physical activity, eating behaviors, and child weight status; (2) 12 family classes that reduce reading demands and incorporate numerous non-print education strategies, hands-on demonstrations, and pictorial instructions (each 2-hour class will be split evenly

IRB-HSR # 19748: A randomized-controlled trial to compare the reach, effectiveness and maintenance of two family-based childhood obesity treatment programs in a medically underserved region

between nutrition, exercise, and behavior change topics); (3) 12 IVR calls that provide reinforcement of class objectives, personalization of goals, and apply teach-back and teach-to-goal methods (two versions of each call will be used—one call for families that attended the class and one for those that did not); (4) 48 family exercise sessions to promote practice and mastery and encourage social support (six PA sessions are integrated within the family class for a total of 2 sessions/week); and (5) bi-weekly child newsletters to reinforce class messages and provide fun family activities. To increase the duration and contact after the initial 24 weeks, we will continue with a 6-month maintenance program, including bi-weekly IVR calls to parents and newsletters to children. The IVR structure will focus on relapse prevention through the reinforcement of program content and skill building opportunities while also allowing for goal setting and feedback relative to nutrition and physical activity outcomes.

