Secondary Aim #4: At each time point, those who drop out of the study will be compared on key demographic variables with those retained in order to understand the mechanism of participation both by group mean tests and by selection bias testing in selection models. Different adherence/attendance to classes and phone calls will be summarized following similar usage metrics by Donkin including a composite measure of exposure (i.e., exposure=intensity x frequency x duration).¹⁰⁴ Both ANOVA and selection models that handle and test potent nonrandom dose exposure resulted from natural choices will be used to analyze dose responses.

6. Have you been working with a statistician in designing this protocol?

Yes

IF YES, what is their name?

[name], Associate Professor at Virginia Tech

7. Will data from multiple sites be combined during analysis?

No

Information from Outside Institution

1. List the names of outside institutions that will be supplying data and/or specimens for this study.

Contact and eligibility information of children are being provided by SOVAH Pediatrics and Piedmont Access to Health Services (PATHS) by review of medical records (see file: Tracking eligible children), but no other data is being provided by SOVAH Pediatrics or PATHS.

The University of Nebraska Medical Center (UNMC) is responsible for developing and managing the web-based platform for the collection of self-reported behavioral and quality of life data from parents and children. However, UNMC is not screening or enrolling participants at their site, there only a single Danville site for this study.

2. Describe the type of information you will receive from each site.

SOVAH Pediatrics and PATHS will provide the research team with contact information and basic demographics for eligible children who are between the ages of 5-12 years and >85th %ile BMI: name, address, phone, birthdate, gender, race/ethnicity, type of insurance. The web-based platform developed by UNMC will include: eating and physical activity habits, health status, quality of life, and perceptions of the home environment.

3. Does the outside institution have an IRB?

Yes, University of Nebraska Medical Center has an IRB. De-identified data will be sent to UNMC under contract.

IRB-HSR # 19748: A randomized-controlled trial to compare the reach, effectiveness and maintenance of two family-based childhood obesity treatment programs in a medically underserved region

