A letter of support is provided from SOVAH Pediatrics and PATHS.

Biomedical Research

1. What will be done in this protocol?

Parent/Child Dyads.

Families have an equal chance of being randomly assigned to any one of the two programs. They cannot choose to which program they are assigned.

GROUP 1: iChoose

The iChoose program will last for 12 months. During the first six months families will be asked to:

- Attend 12 small group education sessions every other week. The health classes are for both the parent and child and will include information on nutrition and exercise.
- Attend one hour family exercise sessions two times a week (total of 48 sessions, 12 of which are part of the small group education sessions)
- Complete 12 automated telephone calls to provide support to help families reach your eating and physical activity goals.
- The child will also get 12 mailed newsletters to help them meet their program goals.

During the last six months of the program parents will continue to get support calls every other week (a total of 12 more calls) and your child will get 12 more newsletters.

See additional study procedures listed in #2 below.

GROUP 2: Family Connections

The Family Connections program will last for 6 months. During this time parents will be asked to:

- Attend 2 education sessions that are one week apart. The health classes are for parents/guardians only and will include information on parental role modeling regarding healthy nutrition and exercise behaviors.
- Complete 10 automated telephone calls to provide support families reach your eating and physical activity goals. There will be 2-3 calls per month during months 1-3 and then 1 call per month during months 4-6.

Community Advisory Board and Parent Advisory Team. Meeting procedures provided above in the study design section. (NOTE: the meetings are not part of the research procedures, only the mixed-methods evaluation, as described below. The participation in meetings is a contractual arrangement for advisory board members).

2. List the procedures, in bullet form, that will be done for RESEARCH PURPOSES as stipulated in this protocol.

IRB-HSR # 19748: A randomized-controlled trial to compare the reach, effectiveness and maintenance of two family-based childhood obesity treatment programs in a medically underserved region

Interventions: The iChoose and Family Connections interventions are described above and in the study design section.

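### The Secondary Aim #4 adherence and exposure measure names only classes and phone calls, so as written it omits the stand-alone exercise sessions that are 60% or 64% of scheduled iChoose+ in-person hours

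*Combined protocol and SAP*

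**What the plan says.** The Brief Summary/Abstract lists as its last secondary aim "4) relative adherence and potential dose response relationships". The analysis is in Statistical Considerations, item 5, Secondary Aim #4: "Different adherence/attendance to classes and phone calls will be summarized following similar usage metrics". The same sentence includes a composite, "i.e., exposure=intensity x frequency x duration". It does not define those three terms for any component, and it does not mention exercise sessions.

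Study Design: Biomedical, item 1, numbers the iChoose+ components separately. The second is "12 family classes that reduce reading demands", the third is the automated calls, and the fourth is "48 family exercise sessions to promote practice and mastery and encourage social support". That section places six of the exercise sessions inside classes.

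Biomedical Research, item 1 (Group 1), also separates the two. The education sessions have one bullet, and another reads "Attend one hour family exercise sessions two times a week". That bullet places 12 of the 48 inside the education sessions.

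In the same two sections, Family Connections consists of two 2-hour parent sessions (called classes in Biomedical Research) and ten automated calls.

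**The concern.** Aim #4 compares adherence between two programs that differ mainly in intensity and duration, and asks whether more exposure goes with more benefit. A measure built on classes and calls covers everything scheduled in Family Connections. In iChoose+ it leaves out the component with the most scheduled occasions. The gap therefore falls on one arm.

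Two results are at stake. The between-arm adherence comparison would not reflect whether iChoose+ families came to the twice-weekly exercise. The dose-response analysis within iChoose+ would give the same exposure to families whose actual participation differed widely.

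**Working it through.** **Inputs.**
- iChoose+ classes: 12 of 2 hours each (Study Design, item 1).
- Exercise sessions: 48 of one hour each, two per week (count in both sections; length from Biomedical Research, item 1).
- Exercise sessions held inside classes: 12 (Biomedical Research, item 1) or six (Study Design, item 1).
- iChoose+ calls: 12 in months 1-6 and 12 more in months 7-12. Call length is not stated.
- Family Connections: two 2-hour sessions and ten calls.

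**1. The plan's own count.** 2 sessions per week x 24 weeks = 48. This reproduces.

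**2. Stand-alone sessions.** 48 - 12 = 36, or 48 - 6 = 42.

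**3. Share of in-person hours not named in the measure.** Class hours are 12 x 2 = 24. The share is stand-alone hours / (24 + stand-alone hours).

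| Sessions inside classes | Stand-alone hours | Total in-person hours | Not counted | Counted |
|---|---|---|---|---|
| 12 | 36 | 60 | 36/60 = 60.0% | 24/60 = 40.0% |
| 6 | 42 | 66 | 42/66 = 63.6% | 24/66 = 36.4% |

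By occasions, the uncounted share is 36/(12 + 36) = 75% or 42/(12 + 42) = 78%.

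**4. Family Connections.** In-person hours are 2 x 2 = 4. All 4 are counted, as are all ten calls.

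**5. Adding call time to the denominator.** Call length is assumed to be 5 to 30 minutes.
- Lowest share: 36 stand-alone hours and 24 calls of 30 minutes (12 hours), 36/(60 + 12) = 50.0%.
- Highest share: 42 stand-alone hours and 12 calls of 5 minutes (1 hour), 42/(66 + 1) = 62.7%.

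Across this range the uncounted sessions are at least half of iChoose+ contact time.

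**6. Consequence for one family.** A family that attends all 12 classes, completes all calls and attends no stand-alone exercise session gets the maximum score. It has received 40% or 36% of its scheduled in-person hours.

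**The case against.** The strongest reply is that the Aim #4 sentence is a summary and does not expressly exclude exercise sessions. Its wording could be shorthand for in-person versus telephone contact. Secondary Aim #1 uses a similar two-way split when it refers to in-person and IVR completion. The sentence also relies on usage metrics from a cited source, which may define more than is printed here.

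It stands that there is no express exclusion. The shorthand reading does not fit the protocol's own usage, however. Classes and exercise sessions are separate items in both descriptions of iChoose+. Some exercise sessions are said to fall inside a class, so the others do not. Each automated call has two versions, depending on whether the family attended the class. Nothing in the documents adds exercise attendance to the exposure.

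Four stronger readings are tempting, and the documents do not support them.

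- **That iChoose+ adherence will be overstated.** The Background (The Challenge of Adherence and Maintenance) says that "programs that include a high number of contact hours over 6 months are associated with low adherence". That compares programs, not components within a program. If exercise and class attendance are similar, the adherence percentage is not inflated.
- **That Family Connections dose is fully measured.** Parent Health Advisor support is planned across both conditions, and Aim #4 names that contact for neither. Only the scheduled classes and calls are fully covered.
- **That 60% or 64% is a share of all contact.** It is a share of in-person hours, since call length is unknown.
- **That the dose-response loss can be stated as a figure.** Let E be the stand-alone hours and r the correlation between class and exercise attendance. With equal SDs of the two attendance proportions, the correlation of class attendance with total in-person hours is (24 + E r)/sqrt(24² + E² + 48 E r). For r = 0.3 to 0.6 and E = 36 or 42 it is 0.67 to 0.85, so an assumed true dose-outcome correlation of 0.30 would appear as 0.20 to 0.25. With r = 0.9 it would appear as about 0.29. The documents give neither r nor the 0.30, and the formula ignores calls and intensity.

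**Conclusion.** The point holds as a defect in the stated measure for a secondary aim. Followed as written, Aim #4 captures 24 of 60 or 24 of 66 scheduled iChoose+ in-person hours, against 4 of 4 in Family Connections. This rests on taking the word classes as the protocol uses it elsewhere and on one hour per stand-alone session. It holds under either printed split.

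The direction of any adherence bias is conditional: upward only if exercise sessions are missed more often than classes. The dose-response analysis within iChoose+ uses an incomplete dose, and the size of any attenuation is unknown. The primary analysis of BMI z-score and the sample size do not depend on this measure.

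**What to change.** In Secondary Aim #4, name three sources for adherence and exposure: classes, stand-alone exercise sessions and phone calls. Define intensity, frequency and duration for each. Report adherence as a share of each arm's scheduled dose.

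Use attendance records already kept. This version is dated 04/22/2020, and the cohort 3 intervention was scheduled to end in 1/2020, with the exercise sessions in its first six months. A new sign-in sheet would therefore probably come too late. The documents do not say whether exercise attendance was recorded. If it was not, label the measure class-and-call exposure and do not interpret it as total program dose or adherence.

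Study Design, item 1, and Biomedical Research, item 1, must be reconciled on how many exercise sessions fall inside classes, because the scheduled total depends on it.

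The cost is a short change to Aim #4 and, where records exist, retrieving and entering them. The downside is that reported iChoose+ adherence may be lower.

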
of those lost to attrition and the reasons for attrition, when at all possible (**MD-4**).

NOTE: Due to COVID-19 social distancing regulations an amendment to this protocol expands questionnaire data collection for parents and children (8 years-12 years) to mailed paper and pencil modality. This modality will only apply to Cohort 3 12 month follow-up data. Assistance with reading the survey over the phone will be offered to those who request this service. Researchers will explore the data for response differences at this time point to help determine any undue impacts from this change.

- Interim analysis will occur after each of the three cohorts complete the 6-month assessment. Early stopping does not clearly apply to this trial, as there are no clear negative consequences. The extensive bibliography provided indicates the value of childhood obesity treatment programs and the minimal risk involved in such programs. Even if the primary outcome (child BMI z-score) does not show statistical improvements, other secondary end points may improve.

3. Provide a justification for the sample size used in this protocol.

Based on the relative BMI z-score differences and standard deviations related to 6-month BMI z-score reduction for *Family Connections* (0.07) and *Bright Bodies* we hypothesize an effect size of 0.73 (moderate to large effect) favoring *iChoose+*. To detect a significant difference between conditions, 58 or 64 children per group are needed to achieve 80% or 85% power with alpha of 0.05, respectively. When considering a typical attrition of 25% in this population, we project a sample size of ~87 participants is needed per condition (n=174 total) to achieve 85% power with approximately 64 dyads/condition completing 6-month assessment. Retention of families in our planning grant is currently 70% at 6-month follow-up.

4. What is your plan for primary variable analysis?

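### Secondary Aim #4 names ANOVA for dose response on a many-valued exposure score without defining dose groups; keeping the score continuous within program is a better and nearly free choice

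*Combined protocol and SAP*

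**What the plan says.** The abstract (Brief Summary/Abstract) gives the last of the secondary aims as "4) relative adherence and potential dose response relationships". The method is under Statistical Considerations, question 5, Secondary Aim #4. Attendance at classes and completion of calls are to be summarized by usage metrics, including "a composite measure of exposure (i.e., exposure=intensity x frequency x duration". The next sentence commits to two methods: "Both ANOVA and selection models that handle and test potent nonrandom dose exposure resulted from natural choices will be used to analyze dose responses".

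The section does not say:
- whether the score is grouped, into how many groups, or at what cut-points;
- which outcome and time point are used;
- whether the two programs are pooled;
- how exposure enters the selection models.

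It gives no power or effect size for this aim. Elsewhere under question 5 the plan uses mixed effect models for Aim #3 and repeated measures ANOVA for Aim #2, so the two kinds of method are named separately.

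**The concern.** ANOVA compares means between groups. A product of three quantities has many values, so a one-way ANOVA on it works only after the score has been divided. Three things follow if that is done:

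- **Power.** Dividing the score discards the variation within groups. With three or more groups the overall test also ignores their order, which is the substance of a dose-response question.
- **Cut-points.** None are fixed, so the answer can depend on a choice left open in the plan.
- **Pooling.** Planned contact differs greatly between programs. Under Biomedical Research, question 1, iChoose has 12 classes, 48 exercise sessions (some inside the classes) and 12 + 12 = 24 calls. Family Connections has 2 sessions and 10 calls. Groups cut from a pooled score would largely sort families by program, so dose and assignment would be mixed.

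At stake is whether a real dose-response within a program would be seen, and whether partners get an estimate per unit of contact that they can use.

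**Working it through.** **The plan's own figure.** There is none for Aim #4. The sample-size section concerns only the primary endpoint and is used here for the number of completers alone.

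**Inputs from the documents.** About 64 completers per condition at 6 months, so 2 × 64 = 128; 130 dyads retained at 12 months; alpha 0.05.

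**Inputs assumed, because the documents give none.** Two-sided test; correlation r between exposure and outcome from 0.10 to 0.50; k = 2, 3 or 4 equal-sized groups; a linear relation; a normal score.

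**Formulas.**
- Regression on the score: F test on 1 and N − 2 df, noncentrality N·r²/(1 − r²).
- ANOVA on k groups: F test on k − 1 and N − k df, noncentrality N·s·r²/(1 − s·r²). Here s is the share of r² that survives grouping, the mean of the squared group means of a standard normal score: 0.637 (k = 2), 0.793 (k = 3), 0.861 (k = 4).

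**Worked case, N = 130, r = 0.25.** r² = 0.0625.
- Regression: 130 × 0.0625/0.9375 = 8.67 on 1 df; power 83%.
- Halves: s·r² = 0.637 × 0.0625 = 0.0398; 130 × 0.0398/0.9602 = 5.39 on 1 df; power 63%.
- Thirds: s·r² = 0.0496; 130 × 0.0496/0.9504 = 6.78 on 2 df; power 63%.
- Quarters: s·r² = 0.0538; 130 × 0.0538/0.9462 = 7.39 on 3 df; power 60%.

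**Both programs together, N = 130.**

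| r | Regression | Halves / thirds / quarters | Loss (points) |
|---|---|---|---|
| 0.10 | 20.6% | 14.8 / 13.4 / 12.2% | 5.8 to 8.4 |
| 0.15 | 40.4% | 27.6 / 25.5 / 23.2% | 12.8 to 17.2 |
| 0.20 | 63.7% | 44.8 / 43.0 / 39.9% | 18.9 to 23.7 |
| 0.25 | 83.2% | 63.4 / 63.0 / 60.1% | 19.8 to 23.1 |
| 0.30 | 94.5% | 79.7 / 80.5 / 78.7% | 14.0 to 15.8 |
| 0.40 | 99.9% | 96.8 / 97.7 / 97.6% | 2.1 to 3.1 |
| 0.50 | 100% | 99.8 / 99.9 / 100% | about 0 |

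**One program, N = 64** (simulation, 4,000 trials per setting; the flat score is bounded, Beta(1.2, 1.2)).

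| r, score | Regression | Halves / thirds / quarters | Loss (points) |
|---|---|---|---|
| 0.30, normal | 68.6% | 49.5 / 46.8 / 43.2% | 19.1 to 25.4 |
| 0.30, flat | 69.1% | 53.7 / 51.5 / 47.7% | 15.4 to 21.4 |
| 0.20, normal | 35.4% | 24.0 / 22.3 / 20.6% | 11.4 to 14.8 |
| 0.20, flat | 34.5% | 26.4 / 23.0 / 20.3% | 8.1 to 14.2 |

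With 64 children the loss falls more slowly as r rises: by the formulas above it is still 5 to 7 points at r = 0.50.

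**Other shapes** (simulation, 1,500 runs, N = 130, r = 0.25 between the outcome and the true dose effect).
- Linear, skewed score: regression 80%, grouped about 50%.
- Threshold at the upper third, normal score: regression 61%, thirds 70%, but halves 54% and quarters 55%.
- Saturating, normal score: regression 56%, grouped 29 to 47%.
- Saturating, skewed score: straight line 33%, grouped 39 to 59%.

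In a separate run of a saturating relation on a skewed score, a straight line had 46%, grouping 61 to 64%, and the regression with a quadratic term 60%.

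**The case against.** The strongest reply is that the plan never says the score will be cut. The product score is one of several usage metrics, and the ANOVA sentence refers to dose responses in general. Some measures are discrete already: attendance at the two Family Connections sessions can only be 0, 1 or 2, and ANOVA on that needs no cut. Its cost is one extra degree of freedom, about 9 to 11 points under a linear relation (N = 64 with r = 0.20 or 0.30; N = 128 with r = 0.245). ANOVA might also be loose wording for a linear model. All of this stands as a limit on the claim. However, the plan names mixed models and ANOVA separately for other aims, and if a linear model is meant the same edit is needed.

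Four stronger readings are tempting and are not supported:
- **That cut-points will be chosen after the data are seen.** The documents leave the grouping open; they do not say this.
- **That ANOVA is the only test, so no slope will be available.** The same sentence commits to selection models, which can carry a continuous exposure and give a coefficient. How exposure enters them is not stated.
- **That Aim #4 is the only analysis bearing on contact intensity.** The randomized programs themselves differ in intensity and duration, and the primary aim compares BMI z between them. Aim #4 is the dose analysis by actual exposure.
- **That a fixed number of power points is lost.** The loss depends on inputs the documents do not give, and under a matching threshold or a saturating relation on a skewed score grouping can win. The threshold advantage appeared only for thirds, whose cut coincided with the threshold.

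**Conclusion.** The concern holds in conditional form. The plan names ANOVA for dose response, the exposure measure it lists is many-valued, and the groups a one-way ANOVA on it would need are undefined. If the score is grouped and the relation is roughly linear, the assumed inputs give a loss of about 13 to 24 points with both programs together (r 0.15 to 0.30) and about 8 to 25 points within one program (r 0.20 to 0.30). These ranges are illustrations, not properties of the plan.

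The practical weight is small. The aim is secondary, the abstract calls the relationships potential, and no power target is set. The better analysis is itself modestly powered within a program: about 35% at r = 0.20 and 69% at r = 0.30 with 64 children. The case for changing is that the alternative is clearer, usually stronger, free of arbitrary cut-points, and yields an interpretable estimate.

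**What to change.** In Secondary Aim #4, replace ANOVA for dose response with a regression or mixed model of BMI z at named time points on the continuous exposure score, adjusted for baseline BMI z. Fit it within program, or jointly with program and a program-by-dose term. Then:

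- report the slope with its 95% CI;
- pre-specify a quadratic or spline term as the check for non-linearity;
- state that exposure enters the selection models as a continuous term too, since they remain the plan's means of handling nonrandom dose;
- keep means by dose group as a descriptive display only.

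The cost is a few sentences in the analysis plan and no new data. The small downside is an assumed shape for the main test; the non-linear term guards against it, and in the saturating case above it brought the regression about level with grouping.
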